^f Monitoring and recording of concomitant medications, adverse events (AEs), and serious adverse events (SAEs) will be conducted throughout the study. Concomitant medications given and AEs/SAEs considered related to study assessments that occur following signed informed consent form (ICF) or assent and prior to study drug dosing must be recorded in the CRF. Concomitant medications given and AEs/SAEs that occur after study drug dosing through the Initial Follow-up Period (*i.e.*, Day 56 visit) must be recorded in the CRF. AEs that are ongoing at the end of the Initial Follow-up Period and are considered drug related should be followed until resolution or no resolution is expected.

^g Subjects will be followed to document other anticancer therapies and survival status for two years following administration of Ad-RTS-hIL-12.

^h Females of childbearing potential will have a serum pregnancy test at the Screening Visit and a urine or serum pregnancy test on Day -1 or Day 0, with a negative test result required prior to first dose of study drug (either veledimex [Arm 1] or injection of Ad-RTS-hIL-12 [Arm 2]). Pregnancy tests will be repeated on Day 28.

ⁱ Hematology Panel (Screening, Days 0, 1, 2, 3, 5, 7, 14, and 28): complete blood count, white blood cell count with differential, red blood cell count, hematocrit, hemoglobin, ESR, and platelet count.

^j Coagulation Panel: activated partial thromboplastin time (aPTT/PTT), international normalized ratio, erythrocyte sedimentation rate, and C-reactive protein.

^k Serum Chemistry Panel (Screening, Days 0, 1, 2, 3, 5, 7, 14, and 28): aspartate transaminase, alanine transaminase, lactate dehydrogenase, alkaline phosphatase, creatinine, total bilirubin, total protein, albumin, lipase, amylase, blood urea nitrogen, glucose, sodium, potassium, chloride, calcium, phosphorus, and bicarbonate.

^l Urinalysis Panel (dipstick): appearance, pH, specific gravity, glucose, protein/albumin, blood, ketones, bilirubin, nitrates, and leukocyte esterase. In addition, a microscopic exam for casts, crystals, and cells may be done if clinically indicated.

^m Standard 12-lead ECG; single measurement at each time point. If ECG is normal at screening and subject has no cardiac risk factors, ECG does not need to be done after Day 0.

ⁿ Centralized registration of eligible subjects will be completed after all screening procedures have been completed, and the subject is deemed eligible by Investigator and Medical Monitor prior to first dose of study drug (either veledimex [Arm 1] or injection of Ad-RTS-hIL-12 [Arm 2]), according to a process defined by the Sponsor.

^o Ad-RTS-hIL-12 intratumoral injection should be administered by [REDACTED] injection for Arm 1 subjects and intracranial stereotactic injection for Arm 2 subjects. Because of the potential for toxicity (*e.g.*, fevers, chills, fatigue, and dehydration), administration of prophylactic antipyretics is recommended after injection of Ad-RTS-hIL-12.

^p Each subject will be carefully monitored for any local reactions and/or hypersensitivity reactions following the Ad-RTS-hIL-12 injection and veledimex administration.

^q The first postresection veledimex dose is to be given on Day 1, preferably with food. Subsequent veledimex doses are to be taken QD, in the morning and within approximately 30 minutes of completion of a regular meal. Dosing on Days 2 to 14 should be at approximately the same time of day (\pm 1 hours) as the Day 1 dosing.

^r Study sites must determine compliance of veledimex dosing. Subjects should be instructed to document veledimex dosing compliance in a subject diary, including the time subject took the QD dose, the time subject ate breakfast, the number of capsules taken, whether subject missed any veledimex doses, and reason for any missed doses. At the end of dosing, subject diary and study drug container(s) with any remaining capsules should be returned to the study staff, so that staff can properly assess dose compliance.

^s The PK sampling is to be conducted in accordance with [Table 2](#) for Arm 1 and [Table 3](#) for Arm 2. In the event that blood volume to be drawn on a given study day would exceed the allowable amount, the Principal Investigator and Medical Monitor will discuss and determine the priority of testing to be completed to ensure patient safety.

^t [REDACTED]

^u [REDACTED]

[REDACTED]

[REDACTED]

[REDACTED]

[REDACTED]

[REDACTED]

[REDACTED] be of diagnostic quality. The brain is to be imaged using the same method(s) used throughout the study. Measurable target lesions should be selected and measured per iRANO criteria guidelines for adults, pending issuance of pediatric criteria. Repeat scans to confirm progression should be completed at 4 weeks and preferably again at 12 weeks (per iRANO) after first documentation of progression. Additional tumor response assessments, as well as a posttreatment diagnostic brain biopsy, may be performed at the discretion of the investigator as part of providing standard-of-care treatment in accordance with current iRANO guidelines.

^x The Day 28 (\pm 7 days) and Day 56 (\pm 7 days) MRI scans are required for all subjects, including those with unconfirmed disease progression, to ensure that more slowly declining tumor burden in response to therapy is noted. For 2 years, subjects without confirmed disease progression should continue to have tumor assessments performed every 8 weeks as per standard practice until disease progression has been identified (first documentation) and confirmed (12 weeks after first documentation). MRI scans and reports should be sent to the Sponsor per the Sponsor's defined process.

^y The MRI scan designated on Day 2 has an allowable window of \pm 24 hours and will be considered the baseline scan for tumor response assessments.

^z Additional tumor, blood, and CSF (if available) samples to be collected, if available, as part of standard-of-care procedures. For example, additional CSF samples may be obtained at the time of MRI scans whenever sedation is clinically indicated or if an Ommaya reservoir is implanted.

^{aa} The tumor sample on Day 0 should be collected prior to Ad-RTS-hIL-12 injection.

^{bb} A tumor sample should be collected if there is a concern of pseudo-progression. The biopsy at Day 56 is strongly recommended. Patients should remain on-study for continued follow-up until confirmed progression per iRANO or the patient meets other withdrawal criteria.

^{cc} Every 8 weeks from Day 56.

^{dd} The patient should be contacted every day during the treatment period to discuss clinical status and updates on current/new adverse events. If the patient is discharged prior to Day 14, follow-up may occur via telephone. Successful contact and contact attempts will be documented in EDC.

^{ee} CSF may be collected at time of the time of MRI scans such as if sedation is clinically indicated or if an Ommaya reservoir is implanted. Collection is optional.

^{ff} The site Investigator will communicate with the Medical Monitor during the active dosing period for all subjects on a daily basis regarding clinical status and laboratory values, prior to the patient receiving their daily dose of veledimex, and additionally as clinically indicated.

^{gg} Assessments to be performed on Day 4, Day 5, and Day 6.

^{hh} To be collected as clinically indicated.

Table 2: Arm 1 Schedule of Veledimex Pharmacokinetic Sampling Times

Sample Number	Day 0	Day 1	Day 2	Day 14	Day 15
1	pre-dose ^a	pre-dose ^a	pre-dose ^a	pre-dose ^a	24 hours post Day 14 dose ^b
2	During resection	2 hours post-dose ^b	-	2 hours post-dose ^b	-
3	-	4 hours post-dose ^b	-	4 hours post-dose ^b	-
4	-	6 hours post-dose ^b	-	6 hours post-dose ^b	-

^a ≤ 30 minutes prior to veledimex dose

^b PK Collections: post-dose PK collections will have a ± 30-minute draw window

Table 3: Arm 2 Schedule of Veledimex Pharmacokinetic Sampling Times

Sample Number	Day 0	Day 1	Day 2	Day 14	Day 15
1	-	pre-dose ^a	pre-dose ^a	pre-dose ^a	24 hours post Day 14 dose ^b
2	-	2 hours post-dose ^b	-	2 hours post-dose ^b	-
3	-	4 hours post-dose ^b	-	4 hours post-dose ^b	-
4	-	6 hours post-dose ^b	-	6 hours post-dose ^b	-

^a ≤ 30 minutes prior to veledimex dose

^b PK Collections: post-dose PK collections will have a ± 30-minute draw window

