Upon completion of each cohort, the SRC will meet to review the data collected to determine next steps as described in Section 7.3. Enrollment in Cohort 4 (with the 20 mg assigned veledimex dose) will not commence until the SRC has determined that dosing at the lower level, Cohort 3, did not result in DLTs that would preclude dose escalation.

In addition to recommending the opening of Arm 2 Cohort 3, or dose escalation to Cohort 4, the SRC may also determine if the study should proceed with the Phase II portion (an expansion of an Arm 2 cohort). In the event that the SRC determines that escalation and/or expansion is not warranted, a decision will be made about stopping the investigation. At the discretion of the SRC, the investigation may be continued at a lower dose. Dose escalation, cohort expansion, and de-escalation rules will be followed as defined in Section 7.3 and study stopping rules will be followed as defined in Section 7.10.

Study Drug Dose and Mode of Administration:

Ad-RTS-hIL-12:

Ad-RTS-hIL-12 will be administered by either [REDACTED] injection into residual tumor sites immediately after tumor resection (Arm 1) or by stereotactic injection into the intratumoral site (Arm 2).

Veledimex:

Veledimex will be administered PO. There should be a minimum of 10 hours between veledimex doses.

Arm 1 (Cohort 1) will receive veledimex 3 (\pm 2) hours before the planned craniotomy and will continue veledimex dosing after Ad-RTS-hIL-12 administration for an additional 14 days.

Subsequent veledimex doses (Days 1 to 14) are to be taken QD and at approximately the same time of day (\pm 1 hour) as the Day 1 dosing and within approximately 30 minutes of completion of a regular meal.

Arm 2 (Cohorts 3 and 4) will receive veledimex only after Ad-RTS-hIL-12 administration for 14 days. The first veledimex dose is to be given on Day 1, preferably in the morning and within approximately 30 minutes of completion of a regular meal. Subsequent veledimex doses (Days 2 to 14) are to be taken QD and at approximately the same time of day (\pm 1 hour) as the Day 1 dosing and within approximately 30 minutes of completion of a regular meal.

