Note: Diagnostic brain tumor biopsy is not considered a DLT. Seizures, headaches, fatigue and cerebral or pontine edema are commonly observed in this population and will be recorded according to the grade of toxicity but will not be considered a DLT unless a relationship to study drug is deemed to be the main contributory factor. Transient neurological changes are expected in Arm 2 and will not be considered a DLT unless they last > 10 days.

Expansion cohorts will be allowed in Arm 2 if deemed appropriate by the SRC. If an expansion cohort is implemented, the veledimex dose may be delayed or reduced for individual subjects in the event of toxicity. If $\geq 33\%$ of subjects in the expansion cohort experience DLTs, using the definition in the dose-escalation phase, additional subjects may be enrolled at the next lower dose tested in the dose-escalation phase or at an intermediate dose, as recommended by the SRC. All DLTs must be reported to the Sponsor within 24 hours of Investigator/site awareness.

Definition of Recommended Phase II Pediatric Dose:

The recommended Phase II pediatric veledimex dose will be determined from the Evaluable Safety Population (ESP), as defined below. The recommended Phase II pediatric dose is defined as the dose level below the dose in which $\geq 33\%$ of subjects in the same cohort experience DLTs. If two DLTs occur in the same cohort, subject dosing will stop in the cohort experiencing the DLTs.

Safety Evaluation:

Safety will be evaluated in the Overall Safety Population (OSP) and the Evaluable Safety Population (ESP), as defined below, using National Cancer Institute (NCI) Common Terminology Criteria for Adverse Events (CTCAE) v5.0.

In the DLT evaluation period (Day 0 to Day 28), if any subject experiences a local reaction that requires operative intervention and is felt to be attributable to study drug(s); any local reaction that has life-threatening consequences requiring urgent intervention or results in death and is felt to be attributable to study drug; or any Grade 4 hematologic toxicity, except thrombocytopenia, that is at least possibly related to study drug and lasts ≥ 5 days, enrollment of new subjects will be paused pending review by the SRC.

Safety assessments will be based on medical review of adverse event reports and the results of vital signs, physical and neurologic examinations, electrocardiograms (ECGs), clinical laboratory tests, and

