In addition to recommending dose escalation, cohort expansion, or discontinuation of treatment, as noted above, the SRC may recommend dose de-escalation at any point based on safety review.

Dose De-Escalation

If it is determined that dose escalation or cohort expansion should not proceed, dose de-escalation may be undertaken and the SRC will consider de-escalating the veledimex dose as follows:

- De-escalation by increments of 5 mg from the cohort in which 2 or more DLTs were observed (*e.g.*, 15 mg, de-escalated from 20 mg)
- If there are 2 or more DLTs in the dose de-escalation cohort, the SRC will consider stopping enrollment at that dose and de-escalating the veledimex dose by an additional increment of 5 mg (*e.g.*, 5 mg down from 10 mg) or declaring a previously studied dose level the recommended Phase II pediatric dose

If no DLTs occur among the three subjects in Cohort 1, dosing may proceed to the next cohort, Cohort 3, after the SRC provides their recommendation to proceed (Table 5). In any cohort, if one DLT occurs among the three subjects, three additional subjects will be enrolled. If one or more of the three additional subjects experience a DLT, dosing will stop. The SRC will then convene to evaluate safety, determine if the recommended Phase II dose has been reached per **Section 7.5**, and will decide whether to stop treatment or de-escalate veledimex dosing. The SRC may also seek an *ad hoc* safety evaluation and recommendation by external experts as needed.

Table 5: Dose Escalation and De-Escalation Decision Rules

Subjects with DLTs (Any Dose Level)	Decision Rule	Subject Count
None of the first 3 subjects OR ≤ 1 subject (in the case of a 6-patient cohort) experiences a DLT	Expand current dose level cohort or enroll the next higher dose level cohort (after SRC recommendation).	3 or 6
1 of the first 3 subjects experiences a DLT	Enroll at least 3 more subjects in this dose level cohort. If none of the 3 additional subjects experiences a DLT, expand current dose level cohort or proceed to the next planned dose level cohort (after SRC recommendation).	6

Table 5: Dose Escalation and De-Escalation Decision Rules (Continued)

Subjects with DLTs (Any Dose Level)	Decision Rule	Subject Count

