7.4. Dose-Limiting Toxicity

An event, occurring within the first 28 days (*i.e.*, Day 0 to Day 28) that meets at least one of the following conditions:

- Any local reaction that requires operative intervention and is felt to be attributable to study drug
- Any local reaction that has life-threatening consequences requiring urgent intervention or results in death and is felt to be attributable to study drug
- Any Grade 3 or higher non-hematologic adverse event that is at least possibly related to study drug and lasts ≥ 3 days
- Nausea and vomiting will not be considered a DLT unless at least Grade 3 or 4 and refractory to antiemetics (*i.e.*, defined as symptoms unrelieved by maximal medical support as directed by the PI (per institutional guidelines) in consultation with the medical monitor).
- Grade 3 or higher thrombocytopenia ($< 50,000/\text{mm}^3$) at least possibly related to study drug

- Any Grade 4 or higher hematologic toxicity (except thrombocytopenia) that is at least possibly related to study drug and lasts ≥ 5 days

Dose escalation may be stopped by the Medical Monitor before a DLT is observed, but where the observed toxicities indicate the strong likelihood of unacceptable toxicity at higher doses.

Note: Diagnostic brain tumor biopsy is not considered a DLT. Seizures, headaches, and cerebral or pontine edema are commonly observed in this population and will be recorded according to the grade of toxicity but will not be considered a DLT unless a relationship to study drug is deemed to be the main contributory factor. Transient neurological changes are expected in Arm 2 and will not be considered a DLT unless they last > 10 days.

Expansion cohorts will be allowed in Arm 2 if deemed appropriate by the SRC. If an expansion cohort is implemented, the veledimex dose may be delayed or reduced for individual subjects in the event of toxicity. If $\geq 33\%$ of subjects in the expansion cohort experience DLTs, using the definition in the dose-escalation phase, additional subjects may be enrolled at the next lower dose tested in the dose-escalation phase or at an intermediate dose, as recommended by the SRC. All DLTs should be reported to the Sponsor within 24 hours of Investigator/site awareness.

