7.6. Dose Modification and Dose Delays

Treatment dose delays and dose reductions for individual subjects will be allowed in the event of toxicities, according to the criteria shown in [Table 6](#). If a drug-related Grade 3 or higher AE occurs (excluding nausea and/or vomiting in subjects who did not receive optimal treatment with anti-emetics), the Investigator in conjunction with the Sponsor's Medical Monitor will decide whether the subject will remain on the study. The withheld doses will not be made up; the subject may be allowed to complete dosing according to the remaining schedule.

As mentioned in [Section 7.4](#), fatigue, seizures, headaches, and cerebral or pontine edema are commonly observed in this population and will be recorded according to grade of toxicity, but

will not be considered a DLT unless a relationship to study drug is deemed to be the main contributory factor. If $\geq 33\%$ of subjects experience DLTs, the SRC will convene to determine the course of action. The Medical Monitor or Investigators may request a meeting of the SRC at other times, as deemed clinically indicated.

Table 6: Criteria for Dose Delay and Dose Reduction

Event	Course of Action
Any local injection reaction that requires operative intervention	Hold study drug and contact the Medical Monitor for instructions on resuming dosing
Any local injection reaction that has life-threatening consequences requiring urgent intervention or results in death	Hold study drug and contact the Medical Monitor for instruction on resuming dosing
Any drug-related Grade 3 or higher AE ^a	Hold study drug and contact the Medical Monitor for instruction on resuming dosing

^a Excluding nausea and/or vomiting in subjects who did not receive optimal treatment with anti-emetics

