#### **4.3. Dose Limiting Toxicity (DLT)**

Dose Limiting Toxicities are defined as events that occur during the first 28 days (Day 0 - Day 28) that meets one of the following criteria:

- Any local reaction that requires operative intervention and is felt to be attributable to study drug
- Any local reaction that has life-threatening consequences requiring urgent intervention or results in death and is felt to be attributable to study drug
- Any Grade 3 or higher non-hematologic adverse event that is at least possibly related to study drug and lasts  $\geq 3$  days
- Nausea and vomiting will not be considered a DLT unless at least Grade 3 and refractory to antiemetics
- Grade 3 or higher thrombocytopenia ( $< 50,000/\text{mm}^3$ ) at least possibly related to study drug
- Any Grade 4 hematologic toxicity (except thrombocytopenia) that is at least possibly related to study drug and lasts  $\geq 5$  days

Note: Diagnostic brain tumor biopsy is not considered a DLT.

- Seizures, headache, and cerebral or pontine edema are commonly observed in this population.

- The grade of toxicity will be recorded.
- However, unless a relationship to study drug is documented to be the main contributory factor, the AE will not be considered a DLT.
- Transient neurological changes are expected in Arm 2 and will not be considered a DLT unless they last > 10 days.

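### Fatigue is conditionally exempt from DLT in the synopsis and 7.6 but not in 7.4 or SAP 4.3, and after a second DLT Table 5 allows continued dosing at a level where the text of 7.3 does not

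*Protocol*

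**What the plan says.** **Fatigue.** Four places list events that are common in this disease and count as a DLT only if study drug is judged the main cause. The DLT note in the protocol synopsis has "Seizures, headaches, fatigue and cerebral or pontine edema are commonly observed in this population", and Protocol 7.6 has "fatigue, seizures, headaches, and cerebral or pontine edema are commonly observed in this population". Protocol 7.4 has "Seizures, headaches, and cerebral or pontine edema are commonly observed in this population", and SAP 4.3 has "Seizures, headache, and cerebral or pontine edema are commonly observed in this population". The last two omit fatigue. Section 7.6 presents its list as the one in 7.4. An event that is not listed falls under the general non-hematologic criterion: Grade 3 or higher, at least possibly related, lasting 3 days or more.

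**Two DLTs.** The synopsis, under the definition of the recommended dose, says "If two DLTs occur in the same cohort, subject dosing will stop in the cohort experiencing the DLTs". The text of 7.3 deals with a cohort that has one DLT among three subjects and takes in three more: "If one or more of the three additional subjects experience a DLT, dosing will stop", after which the SRC "will decide whether to stop treatment or de-escalate veledimex dosing". Table 5, in the same section, has a row for two or more DLTs. What it stops is escalation. The SRC then reviews, and one of the recommendations open to it is that the cohort carry on at its current dose. Protocol 7.5 and SAP 4.4 say that escalation stops and are silent on dosing. Elsewhere the synopsis hands these decisions to the body of the protocol: "Dose escalation, cohort expansion, and de-escalation rules will be followed as defined in Section 7.3".

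**The concern.** The occurrence of DLTs is part of the primary endpoint (Protocol 16.3.1, SAP 4.1.1) and drives the 3+3 decision in children. If the four lists differ, the same clinical events give different DLT counts depending on which section the SRC has open. If the text and the table of 7.3 differ, a dose level with two DLTs can be closed under one and kept open under the other. SAP Table 2 shows Cohort 3 enrolling and Cohort 4 still to come, so on the documents these rules govern decisions not yet made.

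The fatigue event is foreseeable. The protocol calls fatigue common in this population, and the notes to its Table 1 name it among the possible toxicities of the vector injection. Fatigue that is possibly, but not mainly, due to study drug is the case that the two pairs of lists classify differently.

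**Working it through.** The plan gives no figure to reproduce here. The check is a comparison of texts plus simple counts.

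**Step 1: which fatigue events are affected.** The event must be Grade 3 or higher, last at least 3 days, and be possibly but not mainly drug-related. Under 7.4 and SAP 4.3 it meets the general criterion and is a DLT. Under the synopsis and 7.6 it is exempt. Fatigue caused mainly by study drug is not exempt in any of the four places.

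**Step 2: what one such event does under Table 5.**

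| Exempted | Counted | Table 5 action if exempted | Table 5 action if counted |
|---|---|---|---|
| 0/3 = 0% | 1/3 = 33.3% | expand or escalate, on SRC recommendation | at least 3 more subjects |
| 1/3 = 33.3% | 2/3 = 66.7% | at least 3 more subjects | escalation stopped, SRC review |
| 1/6 = 16.7% | 2/6 = 33.3% | expand or escalate, on SRC recommendation | escalation stopped, SRC review |

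In the first row, three more subjects treated one at a time with 28 days each (Protocol 7.3) take at least 3 × 28 = 84 days. The documents give no rate for such fatigue, so no probability is attached to any row.

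**Step 3: one DLT in three, then one or more in the next three.** The text of 7.3 stops dosing and leaves the SRC two outcomes, ending treatment or de-escalating. Table 5 stops escalation and adds a third, staying at the same dose. Both involve SRC review. The conflict is over whether that third outcome is allowed.

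**Step 4: size on that path.** The second DLT falls on subject k = 4, 5 or 6. The DLT rate at that moment is 2/k, and filling the cohort to six (an assumption) adds 6 − k subjects:

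- k = 4: 2/4 = 50%, and 6 − 4 = 2 more
- k = 5: 2/5 = 40%, and 6 − 5 = 1 more
- k = 6: 2/6 = 33.3%, and 6 − 6 = 0 more

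Even if the added subjects have no DLT, the full cohort ends at 2/6 = 33.3%. That meets the 33% threshold in the synopsis, 7.5 and SAP 4.4, which puts the recommended dose one level lower. Staying at the level therefore also sits badly with the recommended-dose definition.

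**Step 5: two DLTs among the first two or three subjects.** The stop sentence in the text of 7.3 does not cover this case. The disagreement is between the synopsis, which stops dosing, and Table 5, which does not. Because the synopsis defers to 7.3, Table 5 is arguably the governing rule here.

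**The case against.** The strongest reply on fatigue is that this is a drafting slip. Section 7.6 cites 7.4 for a list that includes fatigue, so the intended list can be guessed. The exemption is conditional, and the affected event is narrow and of unknown frequency. All of that stands. It does not settle the matter, because 7.4 and SAP 4.3 are the sections that define a DLT, and both lack the word. Adding fatigue is also the more permissive choice, so it should not be left to inference.

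On the two-DLT rule, the reply is that the SRC reviews every case and has wide powers. At 33% or more DLTs, 7.6 has it settle what to do and excludes nothing. After a pause for certain serious events, 7.10 lets it decide on further enrollment at the same level. A separate SRC charter exists and is not available here. These provisions show discretion, but they do not say whether staying at the level is open once the text of 7.3 has stopped dosing. The 7.6 sentence adds to the ambiguity. The 7.10 pause can follow a single event, so it is not a rule for two DLTs.

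A reader might infer that the text of 7.3 stops dosing after any two DLTs, and that up to four more children could be dosed in conflict with it. The documents do not support this. Four more would need both DLTs in the first two subjects, a path on which that text says nothing and the synopsis defers to 7.3. Nor does Table 5 order a plain stop at two DLTs; it stops escalation.

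**Conclusion.** The point holds as two contradictions in current operative wording, and it should be fixed before the next SRC review.

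- **Fatigue:** one qualifying event, counted or exempted, changes the Table 5 action at each of three cohort counts. This rests on the wording alone and needs no assumed rate.
- **Two DLTs:** the conflict between the text and the table of 7.3 is confined to one DLT in three followed by another. It concerns 0 to 2 further children if the cohort is filled to six. For earlier double DLTs there is only a mismatch between the synopsis and Table 5.

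A reader might also want the recommended dose redefined as any level that clears the 3+3 rule, or the supratentorial dose objective removed because Arm 1 closed with three subjects. Neither follows. A definition based only on 0/3 or at most 1/6 would still admit a level that later reached 33% or more DLTs in expansion. The objective is worded to cover either population or both, and the protocol already discloses why Arm 1 was limited to one dose.

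**What to change.** (a) Use one exemption list in the synopsis, 7.4, 7.6 and SAP 4.3. The sponsor's clinical lead should confirm whether fatigue belongs on it. Section 7.6 suggests that it was meant to be there, but that is the more permissive choice in a paediatric trial.

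(b) Put one rule in the synopsis, the text of 7.3, Table 5, 7.5 and SAP 4.4: *Two DLTs in a dose-escalation cohort stop further dosing at that level; the SRC then chooses between ending treatment and de-escalation.* Delete from Table 5 the option of staying at the current dose. Make the sentence in 7.6 on the SRC's response to 33% or more DLTs subject to this rule for escalation cohorts.

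The cost is wording in one protocol amendment and in two SAP sections, with no new data or subjects. The real price is that the SRC gives up the option of continuing at a level with two DLTs.
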